## **Background**

Type 1 diabetes mellitus (T1DM) is caused by a T-cell mediated autoimmune destruction of the pancreatic beta cells resulting in an inability of the pancreas to produce insulin, which is required for maintaining glucose homeostasis. 5% of the UK population have diabetes and of those 10% have T1DM. It is expected that the prevalence and incidence of diabetes will continue to increase worldwide (1).

The majority of subjects with T1DM are on multiple daily injections (MDI) of insulin (a basal-bolus regimen), to mimic physiological insulin secretion in response to glucose levels. The insulin dosages are determined by intermittent capillary blood glucose measurements. Continuous subcutaneous insulin infusion (CSII) via a pump provides an alternative form of insulin therapy with the advantage of delivering variable basal rates throughout the day and less injections (2). In addition, there is evidence supporting benefit of subcutaneous continuous glucose monitoring (CGM) with regards to reductions in hypoglycaemia (3, 4). It is well-established that intensive treatment of T1DM reduces the risk of microvascular complications including retinopathy, nephropathy and neuropathy (5). Achieving optimal glycaemic control with intensive insulin treatment is challenging for many T1DM subjects due to the associated risk of recurrent hypoglycaemia (5) which can result in reduced hypo awareness. Severe hypoglycaemia is associated with seizures and death (6, 7).

Structured education is an important and recommended component of the management plan for people diagnosed with T1DM (8). Self-monitoring of blood glucose, carbohydrate (CHO) counting and insulin dose-adjustment are integral parts of the structured education provided.

[figure not shown]
Insulin bolus calculators have been developed to aid insulin dose adjustment, and are currently incorporated in most of the latest commercially available insulin pumps (9) and some glucose meters. The standard insulin bolus calculator consist of a simple algorithm that requires five subject-specific parameters as input to generate a recommended bolus insulin dose:

- (i) current blood glucose (mmol/L)
- (ii) target blood glucose (mmol/L)
- (iii) insulin-to-carbohydrate ratio (grams of carbohydrate per 1 unit of insulin)
- (iv) total grams of carbohydrate in meals
- (v) insulin sensitivity factor (reduction in glucose per 1 unit of insulin)

Other features such as insulin-on-board (amount of active insulin still in the body from previous injections) are often taken into account, and are important in prevention of delivering excess insulin leading to hypoglycaemia.

This clinical trial protocol assesses a novel Advanced Bolus Calculator for Diabetes (ABC4D). The complete integrated system consists of a smartphone that holds the advanced decision support algorithm. The system requires regular updates of cases derived from continuous glucose monitoring (CGM) data. Each new case includes information about the problem (e.g. capillary blood glucose, meal information and physical exercise), solution (recommended insulin dose) and outcome (post-prandial blood glucose).

## ABC4D System

The novel decision support algorithm is based on case-based reasoning (CBR). CBR is an artificial intelligence technique that tries to solve newly encountered problems by applying the solutions learned from solved problems encountered in the past (10).

The CBR algorithm requires the following input for each insulin dose recommendation:

- Time of day
- Capillary blood glucose
- Meal carbohydrate intake (g)
- Type of meal CHO (fast, medium or slow absorption)
- Pre- or post-meal exercise if within 4 hours of the meal (intensity: moderate or intense)

These parameters make up the case problem presented to the CBR algorithm. Using this information the algorithm will find a similar case scenario from the pool of previously encountered cases and recommend an improved solution (insulin dose) to achieve the best possible outcome (post-prandial blood glucose).

The insulin recommendation application runs locally on a standard operating system such as iOS5.x or Android within a commercially available smartphone. It contains the CBR based decision support algorithm as well as information of past successful cases. Opening the decision support application on the smartphone leads to the main menu, which provides a link to the submenu for requesting a new recommendation. Every calculated recommendation needs to be accepted or declined manually, and the latter option requires the user to enter the adjusted amount of insulin that has been delivered. In addition, the main menu enables the user to view logged data such as recent glucose levels, meal/exercise events and previous insulin dose advices. If subjects are having snacks in between main meals they will have the option to introduce this information in the ABC4D graphical user interface, however no insulin recommendation will be given by the ABC4D.

The glucose sensors that will be used throughout the clinical validation studies are the Enlite sensor (CE marked, manufactured by Medtronic) or the Dexcom sensor (CE marked, manufactured by Dexcom). They are subcutaneous sensor which sit just under the skin and sample interstitial fluid using an enzyme electrode. A small voltage is applied across the sensor and a current is fed back to the sensor instrumentation. This current is proportional to the glucose concentration in interstitial fluid and is calibrated against blood glucose a minimum of 12-hourly. In phase 2 and 3 the CGM will be blinded and either calibrated retrospectively using the iPro2 system (CE marked, manufactured by Medtronic) or calibrated in real-time using the Dexcom CGM system (however the CGM will be blinded to the subject). The iPro2 consist of a recorder that will be attached to the Enlite sensor and at the end of 6 days the data will be downloaded to the Medtronic Carelink iPro software. The Dexcom CGM data will be downloaded to the DiaSend/Dexcom Studio software. In phase 4 Dexcom real-time CGM (i.e subjects will be able to see their CGM data at all times) will be used continuously throughout the study. All data will be anonymised.

In order to demonstrate safety and efficacy of the CBR algorithm, an *in-silico* study using the UVa-Padova T1DM simulator (11) was done and showed good results. The simulator was developed from human data and takes into account sensor errors, sensor placement, route of insulin administration and meal-time glucose absorption.

**Trial Objectives, Purpose and Design:** The principal research objectives are to assess the safety, technical proof of concept and efficacy of the ABC4D device in subjects with T1DM. Safety will be assessed by measuring post-prandial glucose for hypo- and hyperglycaemia. This will initially be assessed over 8 hours with two meal challenges, in a controlled clinical environment. Phase 2 will take place over 6 weeks where subjects will be using the ABC4D for bolus calculations in their normal environment. Subjects will have blinded CGM (Enlite sensor, iPro2, Medtronic) throughout the study and the data will be downloaded every week allowing the research team to update the algorithm's case base with new cases from the preceding week. The algorithm will have the capacity to retrieve new cases in an automatic process, but for safety the research team will accept each case manually in phase 1 and 2. The primary outcome in the third and final phase of the study is the change in HbA1c after subjects have used the ABC4D for 6 months. In the 3rd phase of the study, the subjects will have 4 weeks of consecutive CGM, followed by one week of blinded retrospective CGM each month for the remainder time of the study. The CGM data will be downloaded and calibrated retrospectively, allowing the researcher to update the algorithm's case base with new cases on a monthly basis. In phase 3 and phase 4 the retrieval of new cases derived from combined CGM data and data from the ABC4D application will be a semi-automatic process without the research team approving each case. However, the research team will approve the revision summary before updating the case-base.

The final phase (Phase 4) will aim to investigate the efficacy of ABC4D with RT-CGM compared to standard bolus calculator (defined as the bolus wizard within insulin pumps, bolus calculator in glucose meter or the ABC4D app as a standard bolus calculator (without CBR adaptation)) with RT-CGM where the primary outcome is HbA1c at 6 months. RT-CGM will be used throughout the study period in both the intervention and control group.

The study will be conducted over four phases as outlined below:

## Phase 1

**Objective:** To demonstrate safety and technical proof of concept of the ABC4D in a controlled clinical environment

**Methodology** Non-randomised open label study

**Primary outcome:**

Post-prandial hypoglycaemia within 2 hours of insulin administration

**Secondary outcomes:**

Post-prandial glucose at 60 and 120 minutes

Post-prandial area under the curve (AUC) at 120 minutes

Hypoglycaemia at 4-hours post-prandially

Glycaemic risk: LBGI and HBGI

Glycaemic variability: MAGE and CONGA-2

These are validated, published metrics

**Timescale:** Each subject will be in the study for 8 hours. It is anticipated that it will take 2 months to complete the 1st phase.

**Population:** 6 adults with T1DM

**Subject inclusion criteria:**

- Adults  $\geq 18$  years of age
- Diagnosis of T1DM for  $> 1$  year
- On MDI using a basal-bolus insulin regime
- Structured education in previous 3 years
- HbA1c  $\leq 86$  mmol/mol
- No severe hypoglycaemia (defined as needing 3rd party assistance) in previous year

**Subject exclusion criteria:**

- Recurrent severe hypoglycaemia
- Pregnant or planning pregnancy
- Breastfeeding
- Enrolled in other clinical trials
- Have active malignancy or under investigation for malignancy
- Addison's Disease
- Gastroparesis
- Autonomic neuropathy
- Concomitant use of GLP-1 analogues and gliptins
- Visual impairment
- Reduced manual dexterity

**Subject withdrawal criteria:**

- Loss of capacity to give informed consent
- Cessation of MDI of insulin as usual care for T1DM
- Recurrent severe hypoglycaemia
- Terminal illness

Withdrawal will be immediate and subjects will be followed up in the appropriate out-patient diabetes clinic within 4 weeks of withdrawal

**Recruitment** Recruiting will be undertaken in the T1DM clinics at St Mary's Hospital and Charing Cross Hospital campuses of Imperial College Healthcare. Participant information sheets will be given to potential subjects and, after a minimum of 48 hours and following any questions, informed consent will be taken.

**Visit 1: Screening**

- Attend the clinical research unit at 08:00-09:00
- Routine clinical examination
- ECG
- Non-fasting venous blood taken for HbA1c, creatinine, lipids
- Urine for albumin/creatinine ratio
- Urine pregnancy test in female subjects of childbearing age
- CHO counting and hypoglycaemia education revision by a qualified health care professional.
- The basal insulin dose will be reviewed and adjusted if needed.

- Continuous glucose monitor (CGM retrospective/blinded iPro2, Medtronic) placed in the anterior abdominal wall according to manufacturer's instructions. CGM sensor to be worn for 6 continuous days.
- Instructions to subjects to ensure:
  - Capillary blood glucose measurements fasting, pre-meals, post-meals and pre-bed.
  - Food diaries and physical activity record to be kept for 6 days.

### Visit 2: CGM review

- Attend 7 days following visit 1
- Remove CGM, upload data to Medtronic Carelink iPro software, calibration data and review data with subject.
- Recalculate insulin sensitivity factor (ISF) and insulin:CHO ratio (ICR).
- Update the CBR algorithm with subject's clinical parameters and cases derived from the CGM data and diary.

### Visit 3: Assessment of the ABC4D

[figure not shown]
- Attend the clinical research unit fasting at 08:00. Subjects should take their basal insulin as normal the evening before the appointment.
- Clean area and site intravenous 18g or 20g cannula in peripheral vein
- Subject to have breakfast (40g of CHO) at 08:30, lunch (50g of CHO) at 12:30
- The insulin bolus dose for each meal will be calculated using the ABC4D and given to the subject as a subcutaneous injection (Novorapid or Humalog) in the anterior abdominal wall, immediately before the meal.
- Throughout the study period (08:30-16.30) 2.5mL venous blood will be taken every 15 minutes during the first 2 hours post meal and every 30 minutes for the remaining time. The samples will be analysed immediately for glucose concentration using the YSI glucose analyser.
- The ABC4D study will be terminated if venous blood glucose concentrations fall below 3.0mmol/L or above 15mmol/L, or if the subject experiences hypoglycaemia symptoms. Hypoglycaemia will be confirmed by an additional venous blood plasma glucose sample and will be treated according to Imperial College Hospitals NHS Trust Guidelines.
- After 8 hours (at 16:30) of the study the subject can be discharged if glucose concentrations are stable.
- Acceptability questionnaire to be completed.

Usual care will be maintained for diabetes throughout the study. No concomitant medical therapies are contra-indicated, except GLP-1 analogues and gliptins. Support will be offered to any participants who have concerns about their diabetes management.

**Statistics** 6 subjects planned to be enrolled. This is not a randomised study and there are no comparison or control groups. Outcomes from the study are absolutes as described above. The sample size is a realistic number for recruitment and provides robust clinical validation and safety data. The study is not powered to show a change in the primary or secondary outcomes compared with usual care but is an assessment of a new technology.

Missing, unused, and spurious data will be assessed on an individual basis and may be ignored, withdrawn or the visit may be removed from the analysis with appropriate justification adjudicated by the Principal Investigator.

## Phase 1 of ABC4D study: Summary of visits

## Phase 2

**Objective:** To demonstrate safety, technical proof of concept and efficacy of the ABC4D in the subject's own environment

**Methodology** Non-randomised open label study

**Primary outcome:**

Post-prandial hypoglycaemia

**Secondary outcomes:**

- Post-prandial glucose at 60 and 120 minutes
- Post-prandial AUC at 120 minutes
- Hypoglycaemia at 4-hours post-prandial
- Glycaemic risk: LBGI and HBGI
- Glycaemic variability: MAGE and CONGA-2
- Acceptability questionnaire (non-validated)

These are validated, published metrics.

**Timescale:** Each subject will be in the study for 6 weeks. It is anticipated that it will take 4 months to complete the 2nd phase.

**Population** 20 adults with T1DM

**Subject inclusion criteria:**

- Adults ≥18 years of age
- Diagnosis of T1DM for > 1 year
- On MDI using a basal-bolus insulin regime
- Structured education in previous 3 years
- HbA1c ≤ 86mmol/mol
- No severe hypoglycaemia (defined as needing 3rd party assistance) in previous year

**Subject exclusion criteria:**

- Recurrent severe hypoglycaemia
- Pregnant or planning pregnancy
- Breastfeeding
- Enrolled in other clinical trials
- Have active malignancy or under investigation for malignancy
- Addison's Disease
- Gastroparesis
- Autonomic neuropathy
- Concomitant use of GLP-1 analogues and gliptins
- Visual impairment
- Reduced manual dexterity

**Subject withdrawal criteria:**

- Loss of capacity to give informed consent
- Cessation of MDI of insulin as usual care for T1DM
- Recurrent severe hypoglycaemia
- Terminal illness

Withdrawal will be immediate and subjects will be followed up in the appropriate out-patient diabetes clinic within 4 weeks of withdrawal

**Recruitment.**

Recruiting will be undertaken in the diabetes clinics at Imperial College Healthcare NHS Trust, from registered research databases and from interested subjects who contact us. Participant information sheets will be given to potential subjects and, after a minimum of 48 hours and following any questions, informed consent will be taken.

*Subjects who have already participated in phase 1 of the study can also be recruited for phase 2 and they will be re-consented. These subjects will not need re-screening, however they may need to repeat 1 week of CGM using iPRO2 for initializing of the ABC4D at the start of the Phase 2 study, this is at the discretion of the Principal Investigator.*

**Visit 1: Screening**

- Attend the clinical research unit at 08:00-09:00
- Routine clinical examination

- ECG
- Non-fasting venous blood taken for HbA1c, creatinine, lipids
- Urine for albumin/creatinine ratio
- Urine pregnancy test in female subjects of childbearing age
- CHO counting and hypoglycaemia education revision by a qualified health care professional.
- The basal insulin dose will be reviewed and adjusted if needed.
- Continuous glucose monitor (CGM retrospective/blinded iPro2, Medtronic) placed in the anterior abdominal wall according to manufacturer's instructions. CGM sensor to be worn for 6 continuous days.
- Instructions to subjects to ensure:
  - Capillary blood glucose measurements fasting, pre-meals, post-meals and pre-bed.
  - Food record and physical activity record to be kept for 6 days. The subject will be provided with an ABC4D device and will be instructed to enter information about meals and physical activity directly in the ABC4D application. The insulin dose recommendation button will be disabled and subjects will be advised to use their normal insulin regimen.

#### **Visit 2: CGM review and ABC4D start**

- Attend 7 days following visit 1
- Remove CGM, upload data to the Medtronic Carelink iPro software, enter calibration data and review data with subject.
- Recalculate ISF and ICR after CGM and review of different types of carbohydrates.
- Initialize CBR algorithm case base with cases derived from the CGM data.
- Switch on the ABC4D device
- Instructions to subjects to ensure:
  - Capillary blood glucose measurements fasting, pre-meals, post-meals and pre-bed.
  - Accurate subject input of pre-meal capillary blood glucose, pre- or post-meal exercise (moderate or intense), type of meal absorption (fast, medium, slow), carbohydrate (CHO) amount (g) and insulin given if CBR algorithm advice not taken.
  - No correction boluses for 2 hours post-meal unless clinically indicated (CBG >15mM or ketosis)
- A detailed ABC4D user guide will be given to the subject
- CGM (retrospective/blinded iPro2, Medtronic) placed in the anterior abdominal wall according to manufacturer's instructions.
- 24-hour contact numbers for medical and technical enquires and support will be given to subjects.

#### **Visits 3-7: Weekly download of CGM data and algorithm update**

- Attend clinical research unit on day 7 following visit 2 and then day 14, 21, 28 and 35.
- Upload data from the smartphone ABC4D application to the desktop PC and store it in the corresponding folder.
- Remove CGM, upload data to Medtronic Carelink Pro software, enter calibration data. The CGM data will not be disclosed to the subject.

- Export uploaded CGM data to a text file (i.e. csv) and store it in the corresponding folder.
- Using the ABC4D PC application, update the CBR algorithm case base with the uploaded data from the CGM and the data from ABC4D smartphone application. The medical and engineering team will jointly approve the revised case base before being updated in the smartphone ABC4D application.
- New CGM (retrospective/blinded iPro2, Medtronic) placed in the anterior abdominal wall according to manufacturer's instructions.

#### **Visit 8: Final visit at the end of 6 weeks**

Attend clinical research unit

Remove CGM, upload data to Medtronic Carelink iPro software, enter calibration data.

Switch off ABC4D and return device

Acceptability questionnaire to be completed.

[figure not shown]
Usual care will be maintained for diabetes throughout the study. No concomitant medical therapies are contra-indicated, except GLP-1 analogues and gliptins. Support will be offered to any participants who have concerns about their diabetes management.

Subjects using the ABC4D will have the opportunity to call a physician for medical support and an engineer for technical support 24 hours a day throughout the study.

**Statistics** 20 subjects planned to be enrolled. This is not a randomised study and there are no comparison or control groups. Outcomes from the study are absolutes as described above. The sample size is comparable to other technology transfer studies, is a realistic number for recruitment and provides robust clinical validation and safety data. The study is not powered to show a change in the primary or secondary outcomes compared with usual care but is an assessment of a new technology.

Missing, unused, and spurious data will be assessed on an individual basis and may be ignored, withdrawn or the visit may be removed from the analysis with appropriate justification adjudicated by the Principal Investigator.

## Phase 2 of ABC4D study: Summary of visits

## Phase 3

**Objective:** To demonstrate efficacy of the ABC4D

**Methodology** Randomised open-label study

**Primary outcome:**

HbA1c at 6 months

**Secondary outcomes:**

HbA1c at 3 months

Post-prandial AUC at 4 hours and 6 hours

Post-prandial AUC (<3.9) at 4 hours and 6 hours

Episodes of hypoglycaemia within 4- and 6-hours post-prandially

% time in target glucose (3.9-10mmol/l)

% time in hypo- (<3.9mmol/l) and hyperglycaemia (>10mmol/l)

Glycaemic risk: LBGI and HBGI

Glycaemic variability: MAGE and CONGA-2

Change in weight (kg)

Number achieving target HbA1c ( ≤ 53 mmol/mol )

24-hours insulin dose requirements

PAID score questionnaire

DQOL questionnaire

DTSQ Questionnaire

Acceptability questionnaire (non-validated)

These are validated, published metrics.

**Timescale:** Each subject will be in the study for 6 months. It is anticipated that it will take 15 months to complete the 3rd phase.

**Population:** 142 subjects with T1DM, are required to demonstrate an HbA1c difference of 0.6% with  $\alpha$  of 0.05 and 90% power (two-tailed). We aim to screen n=160 and randomise n=80 in each group. This power calculation is based on using a population mean HbA1c of 7.9% with a standard deviation of 1.1.

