### **Visits 3-8: CGM at 1, 3 and 6 months**

*Visits 3, 5, and 7:*

- Attend clinical research unit at start of week 4, 12 and 24 of the study
- New CGM (retrospective/blinded iPro2, Medtronic or Dexcom) placed in the anterior abdominal wall according to manufacturer's instructions.

*Visits 4, 6 and 8:*

- Attend clinical research unit at end of week 4 (7 days after insertion of CGM), 12 and 24 of the study.
- Remove CGM, upload data to Medtronic Carelink Pro software or DiaSend/Dexcom Studio. The CGM data will not be disclosed to the subject.

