### **Clinical review at 1 month, 3 months and 6 months:**

*Review at 1 month (coincides with visit 4):*

- Review of subject's diabetes control including insulin requirements, incidence of hypoglycaemia, exercise, driving etc.

*Review at 3 months (coincides with visit 6):*

- Review of subject's diabetes control including insulin requirements, incidence of hypoglycaemia, exercise, driving etc.
- Random venous blood taken for HbA1c
- Weight (kg)

*Review at 6 months (coincides with visit 8):*

- Review of subject's diabetes control including insulin requirements, incidence of hypoglycaemia, exercise, driving etc.
- Random venous blood taken for HbA1c
- Weight (kg)
- PAID score, DQOL and DTSQ questionnaires to be completed

Usual care will be maintained for diabetes throughout the study. No concomitant medical therapies are contra-indicated, except GLP-1 analogues, SGLT2 inhibitors and gliptins. Support will be offered to any participants who have concerns about their diabetes management.

Subjects in the intervention group using the ABC4D will have the opportunity to call a physician for medical support and an engineer for technical support 24 hours a day throughout the study.

**Statistics** This is a randomised study with an intervention group and a control group. Outcomes from the study are absolutes as described above. 142 subjects with T1DM, are required to demonstrate an HbA1c difference of 0.6% with  $\alpha$  of 0.05 and 90% power (two-tailed). We aim to screen n=160 and randomise n=80 in each group. This power calculation is based on using a population mean HbA1c of 7.9% with a standard deviation of 1.1.

The sample size is comparable to other technology transfer studies, is a realistic number for recruitment and provides robust clinical validation and safety date of a new technology.

[figure not shown]
Missing, unused, and spurious data will be assessed on an individual basis and may be ignored, withdrawn or the visit may be removed from the analysis with appropriate justification adjudicated by the Principal Investigator.

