## Phase 4 of ABC4D study: Overview of study

**The following information applies to all four phases of the study:**

***Potential risks and benefits***

The potential risks and burdens for research participants are as follows:

At the beginning of each phase of the study there is a venous blood test and in addition the 1st phase includes insertion of an intravenous cannula. These have the potential to cause discomfort. This will be minimised by experienced research personnel and appropriate use of equipment.

During the studies, subjects will have a subcutaneous CGM sensor inserted. Sensor insertion can be associated with some discomfort but the insertion devices are spring-loaded with introducers, making the process rapid and often painless. Any discomfort will be minimised by adhering to manufacturer's instructions.

During the time subjects are using the ABC4D there is a risk from the new technology. The ABC4D may suggest an insulin dose too high or too low potentially resulting in hypo- or hyperglycaemia. In the Phase 1 study subjects are closely monitored in a controlled supervised environment to ensure safety of the ABC4D. In addition, subjects will be given contact phone numbers to call a physician for medical support and an engineer for technical support 24 hours a day throughout phase 2 and 3 of the study.

Insulin will be administered subcutaneously by the subject as per their usual basal-bolus insulin regime. The subcutaneous route is the standard route of insulin administration in T1DM irrespective of whether they are on MDI or pump therapy.

It is acknowledged that the clinical schedule is demanding of subject's time and includes frequent visits to the clinical research unit. This inconvenience is necessary to adequately and safely validate the device. We will minimise the burden as much as possible by making every effort to schedule visits around subject's lifestyles, and by being flexible with attendances at the St Mary's, Charing Cross or Hammersmith campuses of Imperial College Healthcare NHS Trust.

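### Neither randomised phase lists severe hypoglycaemia or ketoacidosis as an outcome, so an HbA1c gain would be reported with no defined severe-harm count by arm beside it

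*Combined protocol and SAP*

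**What the plan says.** **Outcomes.** In Phases 3 and 4 the primary outcome is HbA1c at 6 months. The hypoglycaemia entries under Secondary outcomes, identical in both phases, are "Episodes of hypoglycaemia within 4- and 6-hours post-prandially", post-prandial AUC below 3.9 mmol/L, percentage of time below 3.9 mmol/L, and LBGI. Severe hypoglycaemia and ketoacidosis are in neither list.

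**Where severe events do appear.** The inclusion criteria define severe hypoglycaemia by the need for third-party assistance and require none in the previous year. Its recurrence is an exclusion and a withdrawal criterion. Ketosis appears only in the instruction on correction boluses.

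**Stated risk.** Safety is among the principal objectives under Trial Objectives, Purpose and Design, to be judged from post-prandial glucose. Potential risks and benefits states: "The ABC4D may suggest an insulin dose too high or too low potentially resulting in hypo- or hyperglycaemia". The Background states: "Severe hypoglycaemia is associated with seizures and death".

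**Data collection.** Phase 3 ABC4D participants have four consecutive weeks of CGM and then one period in each of weeks 8, 12, 16, 20 and 24. For the sensor insertions in controls the text reads: "Attend clinical research unit at start of week 4, 12 and 24 of the study". Phase 4 uses real-time CGM throughout in both arms. In both phases and both arms, the 1-, 3- and 6-month reviews cover the participant's "diabetes control including insulin requirements, incidence of hypoglycaemia, exercise, driving etc". The Safety paragraph sends adverse events to the ethics committee, the sponsor, the Principal Investigator and the Trust's incident system. A data monitoring committee meets twice a month in Phases 3 and 4.

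**The concern.** The intervention is a dosing algorithm and the primary outcome rewards lower mean glucose. HbA1c can fall because doses are better matched to meals, or simply because more insulin is given. Severe events by arm help a reader judge which, and at what cost. A glucose threshold of 3.9 mmol/L does not record whether someone needed help, and no listed outcome identifies ketoacidosis. As written, a participant could be withdrawn for recurrent severe hypoglycaemia without those events entering any planned comparison.

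Adverse-event reports are a weak substitute in an open-label trial with unequal contact. Phase 3 schedules 16 visits for ABC4D and 8 for controls. Five of the 16 may be replaced by home sensor insertion, leaving 16 - 5 = 11. The 24-hour physician and engineer line is described only for people using ABC4D, in both phases. An arm with more contact may report more events at the same true rate.

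**Working it through.** **1. The plan's own figure.** Inputs from Phase 3, Population: "142 subjects with T1DM, are required to demonstrate an HbA1c difference of 0.6" percentage points, alpha of "0.05 and 90% power (two-tailed"), and a "population mean HbA1c of 7.9% with a standard deviation of 1.1".
n per arm = 2 x (1.960 + 1.282)^2 x 1.1^2 / 0.6^2 = 2 x 10.51 x 1.21 / 0.36 = 70.6, rounded up to 71, so 142 in total. This reproduces the stated size, which is set by HbA1c alone. Power is 90.1% at 71 per arm and 93.2% at the planned 80.

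**2. Phase 3 CGM coverage after treatment starts.** Coverage = periods x days per period / days of follow-up. A period is 6 or 7 days; follow-up is 168 days (24 weeks) or 182 days (26 weeks).

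| Arm | Periods | Lowest | Highest |
|---|---|---|---|
| ABC4D (weeks 1-4, 8, 12, 16, 20, 24) | 9 | 54/182 = 29.7% | 63/168 = 37.5% |
| Control (weeks 4, 12, 24) | 3 | 18/182 = 9.9% | 21/168 = 12.5% |

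Two inconsistencies affect these figures.
- The text for visits 3-6 can be read as placing a sensor at visit 6, which the activity table does not show. Ten periods would give at most 70/168 = 41.7%.
- Trial Objectives, Purpose and Design describes four weeks plus monthly CGM for Phase 3 participants without separating the arms. If that applied to controls, their coverage would also be 29.7-37.5%.

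Coverage stays below half in every variant. Under the visit schedules ABC4D has 9/3 = 3 times the CGM time of controls, so raw episode counts would need a denominator.

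**3. Phase 4.** CGM is continuous in both arms, so step 2 does not apply.

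**4. What whole-period counting could show.** Person-years = 80 x 0.5 = 40 per arm. With zero events the one-sided 95% upper limit is -ln(0.05)/40 = 2.996/40 = 0.075 per person-year; the upper end of a two-sided 95% interval is 0.092. Phase 4 gives both 80 and 90 per group; at 90 the one-sided limit is 2.996/45 = 0.067.

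**5. Power for a comparison.** The documents give no event risks, so these are assumptions. With 80 per arm, power to detect a doubling of 6-month risk is about 11% (2% v 4%), 22% (5% v 10%) or 42% (10% v 20%).

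**The case against.** The best defence is that the plan measures safety as it defines safety. It names post-prandial glucose as the safety measure, and Phases 3 and 4 list several such measures. The stated objective of those phases is efficacy; safety is the stated objective of Phases 1 and 2. Oversight is not absent either: the data monitoring committee meets twice a month, and the management team reviews events after each phase. No analysis method is given for any outcome, so the lack of a between-arm summary is not peculiar to harms. Entry excludes people with a severe episode in the past year, so events should be few.

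Much of this stands, and it rules out several stronger readings.
- A reader might infer that hypoglycaemia is measured only by CGM. The outcome list names no data source, capillary readings are taken, and both arms are asked about hypoglycaemia at reviews.
- A reader might treat the Phase 3 weeks without CGM as having no hypoglycaemia outcome. They are sampled: both arms have CGM in weeks 4, 12 and 24, which can estimate time below range. Sampling fails for rare events.
- A reader might take the Background to rank severe hypoglycaemia as the main barrier to control. It says only that the risk of recurrent hypoglycaemia makes good control hard for many.

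What the defence does not meet is that post-prandial glucose cannot identify either severe event, and that no document gives the committee or the final report a defined count by arm.

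**Conclusion.** The gap is real in both randomised phases and worth closing. It is a missing safety outcome, not an absence of safety monitoring. In Phase 3 it is aggravated by CGM covering about 30-38% of follow-up with ABC4D and 10-13% in controls, provided that the visit schedules, rather than the undivided description under Trial Objectives, Purpose and Design, are what will be done. In Phase 4 only the missing outcomes count. The sample size is not in dispute.

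A reader might expect the added outcomes to settle whether an HbA1c gain came at the price of severe events. They would not: at 80 per arm the comparison is descriptive. The limit of about 7.5 per 100 person-years assumes zero events, complete six-month follow-up and a Poisson count, and the documents offer no benchmark for it. The added outcomes would give a comparable count, which the present lists cannot.

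**What to change.** In Phases 3 and 4:
- Add two descriptive safety outcomes: severe hypoglycaemia, using the protocol's third-party-assistance definition, and ketoacidosis, with a definition that the sponsor fixes in advance (the documents have none).
- Ask about both in the same words, in both arms, at the existing 1-, 3- and 6-month reviews, covering the whole interval since the last review.
- Count events from randomisation to month 6 or last contact in everyone randomised, including events that lead to withdrawal, with person-time to the same point.
- Report by arm the number of people affected, events per person-year, and the rate difference with an exact interval of a pre-named method, beside the HbA1c result. Giving people as well as events shows when one participant contributes several.
- State that these comparisons are not powered.
- Reconcile the two descriptions of Phase 3 CGM, and give any CGM episode count per unit of sensor time.

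The cost is two case report form questions at visits already scheduled and one table. No visit or participant is added. Some withdrawn participants may miss later reviews, which is why counting stops at last contact; the table should show how many did.
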